#### 2. Introduction

LY3209590 is a long-acting insulin receptor agonist in development for the once-weekly treatment of hyperglycemia in people with T2D and T1D.

### 2.1. Study Rationale

This Phase 3 study will evaluate the efficacy and safety of LY3209590 administered weekly as a fixed dose escalation compared with daily administration of insulin glargine in insulin-naïve adult participants with T2D who are starting basal insulin therapy for the first time. The fixed dose escalation is a simplified dose escalation scheme using 4 set doses of 100 U, 150 U, 250 U, and 400 U of LY3209590, with treat-to-target dose adjustments after at least 4 weeks at each step to achieve the glycemic goals of FBG between 80 and 130 mg/dL.

This study will inform the clinical development of LY3209590.

## 2.2. Background

#### Current state of diabetes care

Most people with diabetes are not achieving glycemic targets. For example, only about one quarter of patients with T2D on insulin and only about 30% of patients with T1D achieve the target glycated HbA1c of 7% and 7.5%, respectively (Blonde et al. 2019; UK National Diabetes Audit 2017).

Treatment complexity, fear of hypoglycemia, delays in insulin initiation and intensification, and suboptimal dosing may pose challenges to diabetes care. There is a need to overcome barriers to dose optimization with basal insulins that provide simple dosing algorithms, rapid achievement of glycemic targets, and a predictable profile with low likelihood of contributing to hypoglycemia.

### Potential for improved treatment regimens and compliance

Once-weekly insulin using a fixed dose escalation could reduce treatment complexity, result in earlier adoption of insulin therapy that may improve treatment compliance, and lead to better real-world patient outcomes. Weekly insulins with a lower peak-to-trough profile during the week and a nearly flat insulin profile could also reduce within-day glucose variability and result in more consistent and predictable glycemic control (Heise 2021).

#### LY3209590

LY3209590 is a novel insulin receptor agonist that is in development as a once-weekly basal insulin for the treatment of hyperglycemia in patients with T2D and T1D. LY3209590 has the potential to decrease patient burden, overcome barriers to initiation of insulin therapy, and may improve glycemic control and quality of life for these patients.

A detailed description of the chemistry, pharmacology, nonclinical and clinical efficacy, and safety of LY3209590 is provided in the IB.

#### Summary of clinical results

A total of 5 clinical studies, in healthy participants and participants with T2D, have been completed to assess the PK/PD, safety, and efficacy of LY3209590. The results thus far support continued development of LY3209590 as a treatment for diabetes mellitus.

Pharmacokinetic and pharmacodynamic results

Single-ascending doses of LY3209590 lowered fasting glucose in a dose- and concentration-dependent manner, with a prolonged time-action profile.

After multiple ascending doses over 6 weeks, maximum concentration and weekly area under the concentration curve (AUC) increased proportionally with dose.

LY3209590 pharmacokinetics show a low peak-to-trough ratio and extended half-life that supports once-weekly dosing.

Phase 2 clinical study results

Available results from Phase 2 studies I8H-MC-BDCM, I8H-MC-BDCL, and I8H-MC-BDCP reflect the potential advantage of having a more stable insulin exposure and less glycemic variability with a long-acting insulin receptor agonist like LY3209590. All studies were openlabel and degludec was the active comparator.

The choice of study population in this study is supported by available efficacy and safety data from Study BDCL, conducted in insulin-naïve participants with T2D.

### Phase 2 Study BDCL results

Study BDCL was a randomized, open-label, comparator-controlled, treat-to-target study evaluating the efficacy and safety of LY3209590 compared with insulin degludec. Study participants had T2D, were insulin naïve, and treated with a stable dose of metformin, alone or in combination with a stable dose of a DPP-4 inhibitor and/or an SGLT2 inhibitor, for at least 3 months prior to screening.

Participants randomly assigned to LY3209590 achieved very good glycemic control during 26 weeks of treatment. LY3209590 demonstrated noninferiority versus degludec for HbA1c change from baseline with both treatment groups achieving a mean HbA1c <7% at study endpoint and participants spending on average more than 75% of their glucose Time in Range70-180.

In this open-label study, there was a low occurrence of hypoglycemia and reported TEAEs were similar during treatment with LY3209590 compared with degludec. In general, the observed safety data were consistent with expectations for insulin in this population. LY3209590 was well tolerated, and no safety findings emerged from the study that would prevent further clinical development.

### 2.3. Benefit/Risk Assessment

Detailed information about the known and expected benefits and risks and reasonably expected AEs of LY3209590 may be found in the IB and that of insulin glargine may be found in the local product package insert.

#### 2.3.1. Risk Assessment

### Potential risks for this study

The potential risks associated with LY3209590 include

- hypoglycemia
- hyperglycemia
- hypersensitivity reaction
- injection-site reactions, for example, injection-site rash, erythema, pruritus, or lipohypertrophy
- immunogenicity, and
- cardiovascular risks.

It is expected that the known risks would be similar to other insulins.

Safety data available to date suggest that there is no increased risk to participants' safety with LY3209590 treatment compared to insulin glargine.

Use of a standard fixed dose escalation for insulin dose adjustment is novel and, to date, untested.

#### Management of risks

Sections 5.1, 5.2, 6.1.2, and 8.3 address known potential risks associated with LY3209590.

#### Protocol risk management measures

Participant education for hypoglycemia

After signing informed consent, all participants will be educated about signs and symptoms of hypoglycemia, how to treat hypoglycemia, and how to collect appropriate information for hypoglycemia. Hypoglycemia may be identified by spontaneous reporting of symptoms from participants, whether confirmed or unconfirmed by simultaneous glucose values, or by blood glucose samples collected between study visits.

Monitoring of participant blood glucose levels

Each participant will have a study-provided glucometer that will wirelessly transfer participant SMBG to their study-provided e-diary. Participants should use the glucometer whenever hypoglycemia is experienced or suspected and check glucose values. The use of personal glucometer or continuous glucose monitoring is not permitted.

A web-interface and reporting system will be available for use by study personnel to view participant e-diary entries, including SMBG, insulin doses, and hypoglycemia information throughout the study. Automated alerts will be transmitted to the investigator any time the participant reports a potential severe episode of hypoglycemia, defined as requiring assistance due to neurological impairment, in the e-diary.

Dose modification and rescue therapy

The dosing regimen used in the study requires the investigator to adjust the insulin dose based on participant FBG and hypoglycemia events (see Section 6.5). The justification for the treat-to-target dosing regimen is detailed in Section 4.3. As modifications of the basal insulin dose may

be influenced by other clinical circumstances or safety considerations known to the investigator, the investigator may prescribe a dose other than the regimen recommended dose. If the investigator prescribes a dose other than the regimen recommended dose, the investigator is responsible for documenting the clinical rationale for the prescribed dose.

Participants will be monitored for persistent, severe hyperglycemia and will receive rescue therapy if this should occur (see Section 6.1.2).

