#### Level 3 Severe

A severe hypoglycemic event is characterized by altered mental or physical status requiring assistance of another person to actively administer carbohydrate, glucagon, or other resuscitative actions for the treatment of hypoglycemia.

The determination of an episode of severe hypoglycemia is made by the investigator based on the medical need of the participant to have required assistance and is not predicated on the report of a participant simply having received assistance.

Examples of severe hypoglycemia in adults are

- altered mental status and the inability to assist in their own care
- semiconscious or unconscious, or
- coma with or without seizures.

Glucose measurements may not be available during such an event, but neurological recovery attributable to the restoration of glucose concentration to normal is considered sufficient evidence that the event was induced by a low glucose concentration.

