# Reporting of severe hypoglycemic events

If a hypoglycemic event meets the criteria of severe, the investigator must record the event as serious on the AE CRF and report it to Lilly as an SAE.

The investigator should also determine if repeated or prolonged episodes of hypoglycemia occurred prior to the severe event.

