#### 4.6.2.1.2. Persistent-Recurrent Hypoglycemia

The potential risk of persistent-recurrent hypoglycemia (P-R hypoglycemia) will be assessed from the first dose date up to the end of the study and will be based on two approaches to identify persistent-recurrent hypoglycemic events:

- 1. using investigator assessment and clinical judgment to determine if repeated hypoglycemia may have contributed to a hypoglycemic event that degenerated with poor outcomes, and
- 2. using a prespecified criteria to derive events from e-diary database (see definition in Appendix 10 (Section 6.9).

Identification of P-R hypoglycemia based on investigator reporting is precipitated by a hypoglycemic event a participant or their caregiver inform having resulted in a poor outcome. This information will trigger an e-mail alert notifying the investigator to contact the study participant, obtain more information about the specific hypoglycemic event, and provide them clinical guidance, if appropriate. Hypoglycemic events that trigger alerts to investigators are those participants or caregivers report in the e-Diary have required treatment with glucagon or IV glucose, resulted in coma, motor vehicle accident or other trauma, hospitalization, or emergency medical care.

Upon receiving the e-mail notification, investigator will access the e-Diary database and answer the following question: "In your clinical judgement, is this hypoglycemia event associated with repeated hypoglycemia events?". Investigator should select "Yes" or "No" as an answer.

During protocol training, investigators are trained to consult the e-Diary database and review participant's blood glucose values and hypoglycemia reports to determine the best answer. If investigator judges the hypoglycemic event that triggered an alert is related to repeated episodes of hypoglycemia, the participant will be identified as having presented a P-R hypoglycemic event reported by the investigator.

P-R hypoglycemia events and participants who present P-R hypoglycemia will be identified by one or both approaches explained above. Summary statistics and a listing of the events identified by both methods will be provided.

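### Protocol and SAP define the e-diary hypoglycemia alert differently; under the SAP's list, a severe episode treated by another person with carbohydrate alone cannot be counted as investigator-identified persistent-recurrent hypoglycemia.

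*Protocol*

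**What the plan says.** Protocol 2.3.1, under the risk-management measures, states: "Automated alerts will be transmitted to the investigator any time the participant reports a potential severe episode of hypoglycemia". It qualifies such an episode as "defined as requiring assistance due to neurological impairment, in the e-diary" and sets no condition on how the episode was treated or how it ended.

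Protocol 8.3.6 characterizes a Level 3 event by altered mental or physical status "requiring assistance of another person to actively administer carbohydrate, glucagon, or other resuscitative actions for the treatment of hypoglycemia". Carbohydrate actively given by another person is therefore enough. The investigator decides whether an event is severe, and a participant's report of having received help does not settle it. For events that meet the criteria, the same section requires reporting as an SAE and adds: "The investigator should also determine if repeated or prolonged episodes of hypoglycemia occurred prior to the severe event".

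SAP 4.6.2.1.2 describes the alert differently: "Hypoglycemic events that trigger alerts to investigators are those participants or caregivers report in the e-Diary have required treatment with glucagon or IV glucose", or that "resulted in coma, motor vehicle accident or other trauma, hospitalization, or emergency medical care". On receiving the e-mail, the investigator answers a yes/no question on whether the event is associated with repeated hypoglycemia. The classification follows from that answer: "If investigator judges the hypoglycemic event that triggered an alert is related to repeated episodes of hypoglycemia", the participant is identified as having an investigator-reported persistent-recurrent event.

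SAP 4.6.3.1 counts Level 2 and Level 3 events as clinically significant and describes the investigator route as an assessment of clinically significant events. Its analysis table compares the number of participants with at least one investigator-identified event by Fisher's exact test. A separate row covers events found by the programmed search in Appendix 9 (Section 6.9).

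**The concern.** The two documents do not describe the same set of alert-triggering events, and the difference reaches an analysis. In the SAP the alert is the only way into the investigator-identified category. A participant with a severe episode that triggers no alert appears in that row as having no event, which is indistinguishable from an investigator having looked and answered no.

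Persistent-recurrent hypoglycemia is a named safety topic of interest in the SAP. It matters here because Protocol 6.9 gives LY3209590 a half-life of about 17 days and Protocol 2.3.1 calls the fixed dose escalation novel and untested. The investigator route is also the one suited to judging whether repeated lows led up to a severe event, which is what Protocol 8.3.6 asks the investigator to determine.

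**Working it through.** The documents give no figure to reproduce and no arithmetic applies. The check follows one hypothetical episode through each text.

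**Test episode.** Over several days a participant has repeated Level 1 lows. The participant then becomes neurologically impaired, and another person actively gives carbohydrate by mouth. No glucagon or IV glucose is used, and there is no coma, accident, other trauma, hospitalization or emergency care. The participant recovers and has no further lows. The investigator confirms a Level 3 event.

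| Step | Source | Result |
|---|---|---|
| Is it Level 3? | Protocol 8.3.6 | Yes: another person actively gave carbohydrate |
| Does it meet the protocol's alert definition? | Protocol 2.3.1 | Yes: assistance was required because of neurological impairment |
| Should the investigator look for earlier repeated or prolonged episodes? | Protocol 8.3.6 | Yes, as for any severe event |
| Is it clinically significant in the SAP's terms? | SAP 4.6.3.1 | Yes: Level 3 |
| Is it on the SAP's trigger list? | SAP 4.6.2.1.2 | No: neither the treatment nor any outcome is listed |
| Is the persistent-recurrent question asked? | SAP 4.6.2.1.2 | No: it follows receipt of the alert e-mail |
| Can it enter the investigator-identified row? | SAP 4.6.3.1 table | No |

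**Does the programmed search recover it?** Appendix 9 looks forward. The set must start with a Level 2 or Level 3 episode, be followed by more episodes on the same day, and then by at least one per day over the next 2 days or longer. In the test episode the earlier lows are all Level 1, so none can start a set. The Level 3 event could start one, but nothing follows it. The search does not find it. A different pattern, such as a Level 3 event followed by lows that day and on the next two days, would be found however it was treated.

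**Does the Protocol 8.3.6 determination recover it?** Neither document says that this determination feeds the SAP category.

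**What does not depend on the alert?** Severe events must be recorded as serious and reported as SAEs (Protocol 8.3.6). Level 3 incidence and rate (SAP 4.6.3.1), the severe hypoglycemia listing (SAP 4.6.2) and the programmed persistent-recurrent row stand as they are.

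**The case against.** The strongest reply is that two alerts exist with different purposes. Protocol 2.3.1 describes a general safety alert. The SAP's alert sits inside the persistent-recurrent section, and its stated aim is events that deteriorated to a poor outcome. On that reading, leaving out recoveries after carbohydrate alone is a deliberate choice of scope. Persistent-recurrent hypoglycemia is also not among the listed objectives, so no protocol-defined endpoint is broken. This reading is possible, but neither document states it. SAP 4.6.3.1 describes the investigator route more broadly, and SAP 4.9 says that nothing in the protocol-planned analyses has changed. Even with two alerts, the Protocol 8.3.6 determination would still have no place in the analysis.

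Three stronger readings might be inferred, and the documents do not support them:

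- **That investigators will not be alerted to these episodes.** That depends on the e-diary specification, which is not in the documents. If the protocol's broader alert is implemented and also opens the question, no episode is missed and the SAP text is what needs correcting. Designated site personnel can in any case view e-diary hypoglycemia entries at any time (Protocol 8.3.6).
- **That these episodes drop out of the persistent-recurrent analysis altogether.** SAP 4.6.2.1.2 accepts identification by either approach, and the programmed search needs no alert.
- **That a large share of the count is lost.** The documents give neither a Level 3 rate nor the proportion treated with carbohydrate alone. Moreover, only those episodes that an investigator would link to repeated lows could be lost, not every unasked Level 3 event.

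**Conclusion.** The inconsistency is real and affects one Fisher-tested safety row. As the SAP is written, a confirmed Level 3 episode treated by another person with carbohydrate, with no listed treatment or outcome, cannot be investigator-identified as persistent-recurrent, whatever the investigator finds under Protocol 8.3.6.

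The size cannot be stated from the documents. The loss in this row is at most the number of such episodes that an investigator would judge related to repeated lows. Some of those may still appear in the programmed row, and the loss may be zero. The conclusion assumes that the SAP's trigger list is complete as worded and that the question is opened only by the alert, which is what SAP 4.6.2.1.2 says.

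The correction is worth making because it is specific and cheap, and it improves ascertainment of a prespecified safety topic. It does not call the Level 3 results into question.

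**What to change.** 1. Reconcile Protocol 2.3.1 with SAP 4.6.2.1.2. State whether there is one alert or two, list the triggers of each, and say which of them opens the persistent-recurrent question.
2. In SAP 4.6.2.1.2, take the Protocol 8.3.6 determination, recorded as yes or no, as the investigator's answer for every investigator-confirmed Level 3 event, in addition to the events already listed. Where the e-diary has not captured it, obtain it by site query. Because the study is open-label, put the same question to all confirmed Level 3 events in both arms.
3. Base the addition on investigator-confirmed Level 3 events. A trigger of any reported assistance would be wider than Protocol 2.3.1, which requires neurological impairment, and would sit badly with Protocol 8.3.6, under which receiving help does not by itself make an event severe.

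The cost is SAP wording and a handful of site queries on events already reported as SAEs. The investigator-identified category becomes slightly broader than the SAP's poor-outcome framing, and the report should say so. No dose or clinical management rule changes.

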#### 2.3.2. Benefit Assessment

Participants may benefit by receiving personal health information, routine safety assessments, and frequent engagement with health care providers during the study, which provide opportunities for coaching and support.

Participants may benefit from the improvement of glycemic control promoted by basal insulin. The weekly administration of LY3209590 has the potential to offer a more consistent glycemic control, while the fixed dose escalation regimen may represent a simple way to initiate insulin treatment for the first time.

#### 2.3.3. Overall Benefit Risk Conclusion

Considering the clinical data to date and measures taken to minimize risk for the participants in this study, the potential risks identified in association with LY3209590 are justified by the anticipated benefits that may be afforded to insulin-naïve participants with T2D.

# 3. Objectives, Endpoints, and Estimands

Objectives	Endpoints
Primary	
Demonstrate noninferiority of LY3209590 compared to insulin glargine for the treatment of T2D in adults	Change in HbA1c from baseline to Week 52
Key Secondary (Gated)	
Demonstrate superiority of LY3209590 compared to insulin glargine	Change in HbA1c from baseline to Week 52
Other Secondary	
Compare the effect of LY3209590 to insulin glargine in parameters of glycemic control	
 
Change from baseline to Week 26 for HbA1c
 
Change from baseline to Weeks 16, 26, and 52 for fasting glucose measured by SMBG
 
Insulin dose at Weeks 16, 26, and 52
 

Compare the effect of LY3209590 to insulin glargine on safety endpoints	
 
Incidence and rate of composite of Level 2 and 3 hypoglycemia events during the treatment period
 
Incidence and rate of composite of Level 2 and 3 nocturnal hypoglycemia events during the treatment period
 
Change from baseline to Weeks 26 and 52 in body weight
 

Compare the effect of LY3209590 to insulin glargine on patient-reported outcomes questionnaires	
 
Change from baseline to Weeks 26 and 52 for 
 
TRIM-D, and
 
DTSQ
 
 
 
Treatment experience at Weeks 26 and 52 for 
 
DID-EQ, and
 
SIM-Q.
 
 
 

Tertiary	
Compare the effect of LY3209590 to insulin glargine for efficacy parameters	Percentage of participants at Week 52 achieving
Evaluate the percentage of participants receiving LY3209590 that require a transition to the LY3209590 prefilled pen	Percentage of participants that require transition to the LY3209590 prefilled pen at Weeks 26 and 52
Evaluate the percentage of participants at each fixed LY3209590 dose level	Percentage of participants at each fixed dose level at Weeks 26 and 52
Compare the effect of LY3209590 to insulin glargine for safety parameters	
 
Incidence and rate of Level 2 hypoglycemia events during treatment period
 
Incidence and rate of Level 3 hypoglycemia events during treatment period
 
Incidence of positive LY3209590 treatment-emergent antidrug antibodies
 

Characterize the PK/PD of LY3209590	LY3209590 PK and concentration-response relationships to key safety and efficacy measures
Compare the effect of LY3209590 to insulin glargine on patient-reported outcomes questionnaires	Frequency of responses to Basal Insulin Experience of "likelihood of incorporating into routine"

Abbreviations: HbA1c = hemoglobin A1c; DID-EQ = Diabetes Injection Device Experience Questionnaire; DTSQ = Diabetes Treatment Satisfaction Questionnaire; PK/PD = pharmacokinetics/pharmacodynamics; SMBG = self-monitoring of blood glucose; SIM-Q = Simplicity Questionnaire; T2D = type 2 diabetes; TRIM-D = Treatment-Related Impact Measure – Diabetes.

